3.4. Statistical analysis

3.4.1. Preliminary considerations

All statistical analyses will be performed using SAS v. 9.2. Basic summary statistics will be calculated for all outcome variables and covariates of interest. Continuous variables will be checked for normality using Q-Q plots.

3.4.1.1. Missing data. Analyses will use an intent-to-treat approach that includes all patients randomized. Study procedures have been proposed to minimize loss of data due to withdrawal or loss. However, sensitivity analyses will be employed to assess the impact of missingness and both conservative and liberal imputations will be used.

3.4.1.2. Adjustment for Clustering. Clusters exist within the intervention arm and analyses thus require consideration of the effects due to clustering, assessed by analyzing within- and between-cluster variance as well as estimating the intraclass correlation coefficient using generalized linear mixed effects modeling. The cluster effect will be deemed significant if the appropriate covariance parameter estimate obtained from the model has p -value <0.05 .¹⁴² In this event, rather than using a two-sample, two-sided, z-test to compare proportions between the two treatment arms and the t-test (or the Mann-Whitney test if distributions are sufficiently non-normal) for the comparison of means, the cluster-adjusted chi-square test will be used to compare proportions and the cluster-adjusted t-test (or the cluster-adjusted Wilcoxon Rank-Sum test if distributions are sufficiently non-normal) will be used to compare means. Similarly, rather than using linear regression analysis to analyze relationships between continuous dependent variables and indicated covariates, linear mixed modeling will be employed. Lastly, rather than using logistic regression analysis to assess relationships between dichotomous dependent variables and indicated covariates, generalized linear mixed effects modeling will be employed.

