3.4.2. Data Analysis

Primary Aim 1. In a randomized design, determine the efficacy of the 12-month ELM Intervention, relative to Education Control, in an ethnically diverse sample of MetS patients. We hypothesize that the ELM intervention will produce a clinically significant remission of the MetS in at least 40% of those treated, while the remission rate in the Enhanced Usual Care Arm will not be higher than 15% at 12 months.

For each arm, the proportion of patients in remission of MetS at 12 months will be computed. The appropriate 2-sample test (see 'Adjustment for Clustering' section) will be used to compare the proportions. We will also test the hypothesis that the intervention produces a 12-month MetS remission rate of $\geq 40\%$.

Identification of a clinically significant primary endpoint and threshold on that endpoint is crucial to the determination of whether or not a proposed treatment deserves further testing.¹⁰⁴ The dichotomous rate of MetS remission (i.e., no longer meeting criteria) is the most popular primary endpoint in clinical trials of the MetS.^{92-94, 105-107} A continuous MetS score has not been validated in American adults.^{108, 109}

Secondary Aim 2. To assess the sustainability of the combined ELM plus Extended Maintenance Intervention on remission of the MetS at 24 months. We hypothesize that the ELM intervention will produce a clinically significant remission of the MetS in at least 38% of those treated, while the remission rate in the Education Control arm will not be higher than 15%.

Analytic procedures will be exactly the same as those for the Primary Aim (above).

Secondary Aim 3. To assess the impact of the 12-month ELM Intervention, and the 24-month ELM plus Extended Maintenance Intervention, on intermediate behavioral outcomes (dietary intake, physical inactivity, and stress) and secondary outcomes (body mass index, vitality, and MetS components).

Separate analyses will be conducted for each outcome. Mean changes (from baseline to 12 or 24 months) between the two arms will be compared using the appropriate 2-sample test (see 'Adjustment for Clustering'). The dependent variable will be the respective outcome at 12 or 24 months and the covariate predictors will be the baseline value and treatment allocation.

Exploratory Aim 4. To develop a system for monitoring costs of the intervention and of medical care over 24 months of follow up in all randomized patients.

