3.4.3. Sample Size and Power

The **primary outcome** of the study is remission of MetS from baseline to the 12-month visit. We hypothesize that at least 40% of patients in the Intervention Arm, and no more than 15% in the control arm will achieve remission. This hypothesis is supported by the ELM proof-of-concept study and published data on 12- and 24-month MetS remission rates of 9-14% in both control groups' patients.^{93, 95, 106} The proposed study employs clusters within the treatment arm only. To estimate sample size, adjustments were made for the intra-class correlation coefficient (ICC). Using data from the ELM proof-of-concept study, we conservatively estimate the ICC to be

A two-sample, two-sided, z-test for proportions will be used to compare the rate of MetS remission between the two treatment arms with an overall significance level of 0.05.

The sample size chosen is 48 patients (16/arm). Required sample sizes were computed under several plausible scenarios, indicated by our proof-of-concept study and other relevant studies. Power was set at 80%, alpha was 0.05, and a 20% dropout rate was assumed. **Figure 5** shows that if a sample size of 48 is chosen, there will be adequate power to detect a statistical difference between a remission rate as low as 40% in ELM Intervention arm and as high as 15% in the Education Control arm. Similar sample sizes resulted when the number of participating sites, clusters per site, and patients per cluster (between 10 and 13) were varied. There will be inadequate power to detect an effect if the ELM Intervention effect erodes to below a 38% remission and the Education Control remission rate is as high as

15%. However, this state of affairs would suggest that more developmental work on either the treatment or control group is needed before progressing.

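### ELM-arm clustering is adjusted for only if its variance estimate reaches p<0.05, a pre-test that a handful of groups will usually fail, so the stated 0.05 level is not protected

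*SAP*

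**What the plan says.** SAP section 3.4.1.2 accepts that the design creates clustering: "Clusters exist within the intervention arm and analyses thus require consideration of the effects due to clustering". It then sets a trigger: "The cluster effect will be deemed significant if the appropriate covariance parameter estimate obtained from the model" has a p-value below 0.05. If the trigger is met, a cluster-adjusted chi-square, t or rank-sum test, or a mixed model, is used. If not, the ordinary z-test, t-test (or Mann-Whitney test) and regressions are used. Nothing in the SAP keeps the adjustment after a non-significant result.

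Section 3.4.2 carries the rule into the main analyses:
- **Primary Aim 1:** "The appropriate 2-sample test (see 'Adjustment for Clustering' section) will be used to compare the proportions".
- **Secondary Aim 2 (24 months):** the same procedures as the primary aim.
- **Secondary Aim 3:** "Mean changes (from baseline to 12 or 24 months) between the two arms will be compared using the appropriate 2-sample test", again pointing to the clustering section.

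Section 3.4.3 says that clusters exist in the treatment arm only, that the sample size was adjusted for the ICC, and that the primary comparison is two-sided at an overall level of 0.05.

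**The concern.** Patients treated in the same ELM group share a coach and each other. That correlation belongs to the design, whatever a test of it shows. A non-significant variance estimate from a few groups says little about whether the ICC is zero, yet the plan treats it as grounds for analysing patients as independent. Planning therefore allows for the ICC while the analysis will usually drop it. When a positive ICC is ignored, the standard error is too small and the nominal 0.05 level is exceeded. The primary test also becomes a data-dependent choice between two methods.

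**Working it through.** **Inputs from the SAP.** Trigger p<0.05 (3.4.1.2). Two-sided 0.05, 40% vs 15% remission, ELM-only clusters, 10 to 13 patients per cluster and 20% dropout (3.4.3).

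**Assumed.** ICC of 0.02, 0.05 or 0.10, because the value is not readable. 15% remission in both arms under the null, and equal arms.

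**1. Number of ELM groups.** Section 3.4.3 gives 48 patients but also 16 per arm, and two arms of 16 make 32. If 48 is the total, 24/12 = 2 groups. If 48 is per arm, 48/12 = 4 to 48/10 = 4.8, so 4 to 5 groups. At 16 per arm, 16/13 = 1.2 to 16/10 = 1.6, so 1 or 2 groups.

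**2. Cost of ignoring the ICC.** The design effect in the ELM arm is 1 + (m − 1) × ICC. With equal arms and an unclustered control arm, the variance of the difference is inflated by (design effect + 1)/2. For m = 12:

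| ICC | Design effect | Variance ratio | 1.96/√ratio | Actual two-sided level |
|---|---|---|---|---|
| 0.02 | 1.22 | 1.11 | 1.860 | 6.3% |
| 0.05 | 1.55 | 1.275 | 1.736 | 8.3% |
| 0.10 | 2.10 | 1.55 | 1.574 | 11.5% |

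**3. Simulation of the rule.** There were 200,000 beta-binomial trials per setting (Monte Carlo error about 0.1 point). The SAP does not name the test behind the covariance p-value, so a one-way ANOVA F-test among ELM groups stands in for it. If it is significant, the z-test multiplies the ELM variance by 1 + (m − 1) × estimated ICC. Otherwise the pooled z-test is used. Entries are percentages at ICC 0.02/0.05/0.10.

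| ELM groups | Pre-test detects | Level, plan's rule (at ICC 0) | Level, always adjusted | Favouring ELM, plan's rule |
|---|---|---|---|---|
| 4 of 12 | 9/16/27 | 6.4/7.9/9.9 (5.3) | 5.2/6.4/8.1 | 2.9/3.3/3.4 |
| 5 of 12 | 9/18/32 | 5.6/7.0/8.8 (4.6) | 5.7 at ICC 0.05 | not tabulated |
| 2 of 12 | 5/8/13 | 6.5/8.0/10.4 (5.3) | 5.8/7.1/9.5 | 3.0/3.5/4.0 |
| 2 of 8 | 2/4/7 | 4.9/5.6/6.8 (4.2) | 4.6/5.2/6.3 | 2.3/2.6/3.0 |

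At ICC 0 the rule gives roughly the stated 5%. With a single group of 16 no pre-test is possible, and the plain z-test gives 6.0/8.2/11.6%. With more groups of 12 the excess shrinks: 5.8/6.9/8.1% with 8 groups and 5.5/6.0/6.1% with 24.

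**4. Other settings.**
- 10% remission in both arms (section 3.4.3 cites 9 to 14%): 5.5/6.7/8.1% with 2 groups of 12, and 3.1/3.6/4.2% at 16 per arm.
- 20% dropout (24 per arm becomes about 19, taken as 2 groups of 10): 5.7/7.0/8.6%.
- Continuous outcomes under the rule: 5.8/7.4/9.8% (2 of 12) and 5.9/7.2/8.7% (4 of 12). Always adjusted, these are 4.8/6.1/8.0% and 4.9/5.8/6.9%.

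**5. A different pre-test.** With k balanced groups, a one-sided Wald Z on the moment variance component cannot exceed √((k − 1)/2). The smallest possible p is therefore 0.24 for k = 2, 0.11 for k = 4, 0.079 for k = 5 and 0.057 for k = 6. With six groups or fewer the adjustment could never be triggered. The level at ICC 0.05 is then 8.4 to 8.8% with 2 to 5 groups of 12. This bound was not checked for a binary mixed model.

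**The case against.** The strongest objection is that the pre-test is only part of the problem. With 2 groups of 12, always adjusting still gives 5.8/7.1/9.5%, because two groups cannot estimate an ICC well. Removing the pre-test gains 0.7 to 0.9 point there and 1.2 to 1.8 points with 4 groups. This stands, and the fix must not be presented as restoring 0.05.

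Second, the scenarios are uncertain. Groups of 8 or 16 fall outside the plan's 10 to 13. Only 48 per arm comes near the stated 80% power (79.3% before dropout and clustering, against 49% for 24 per arm), which points to 4 to 5 groups. That reading still shows the excess: 7.9% with 4 groups and 7.0% with 5 at ICC 0.05.

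Third, the effect on a decision to go on with ELM is small. Much of the excess for remission lies in the direction of ELM being worse. False positives favouring ELM with observed ELM remission of at least 40% occur in 0.2/0.5/1.2% of trials with 2 groups of 12, and in at most 0.2% with 4. The SAP plans a test of the 40% hypothesis but does not make an observed 40% a condition of success, so these figures are only a guide. The mean comparisons have no such threshold, and their excess is symmetric.

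Fourth, the F-test is a stand-in for an unnamed test, so the percentages are approximate. The Wald alternative makes the rule look worse.

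**Conclusion.** The concern holds. The adjustment is conditional on a test that will usually miss a moderate ICC at the group counts the SAP implies, and the plan has no fallback. With 2 to 5 groups of 12 and an ICC of 0.05, the two-sided level for remission is about 7 to 8%. At an ICC of 0.10 it is about 9 to 10%. At an ICC of 0.02 the excess is at most about 1.5 points, and at 16 per arm in two groups it appears only from an ICC of about 0.05. These figures rest on assumed ICCs, derived group counts and a stand-in pre-test. The existence of the rule and the direction of the problem with few groups and a moderate ICC are firm, but the exact size is not. The rule should be changed, although it is unlikely on its own to produce a wrong decision in favour of ELM on remission.

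**What to change.** Delete the p<0.05 condition in section 3.4.1.2. Suggested text: *Because ELM is delivered in groups, all between-arm comparisons will account for clustering in the ELM arm, whatever the size or significance of the estimated cluster variance, using the cluster-adjusted tests and mixed models named in this section. The ICC will be reported descriptively.*

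Add a sensitivity analysis of the primary outcome using a design effect based on the planning ICC of section 3.4.3. If only one ELM group forms, the ICC cannot be estimated and the planning value is needed. With an assumed planning ICC of 0.05, the level of this analysis at true ICC 0.02/0.05/0.10 is 3.2/4.4/6.5% (2 groups of 12) and 3.6/5.1/7.8% (4 groups), so it depends on that value being right. The SAP should acknowledge that with so few groups the 0.05 level is approximate.

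The cost is SAP wording, minor programming and a little power. For 40% vs 15%, moving from the plan's rule to always adjusting:

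| ELM groups | Power at ICC 0 | Power at ICC 0.05 |
|---|---|---|
| 2 of 12 | 48.4 to 45.1% | 44.5 to 40.9% |
| 4 of 12 | 78.7 to 75.7% | 71.7 to 67.6% |
| 2 of 8 | 35.8 to 33.4% | 34.3 to 31.7% |

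A small-sample degrees-of-freedom method is optional. If one is used, it should be named in advance and its power stated. A Satterthwaite test on group means has power 28.5% (2 of 12) and 50.8% (4 of 12) at ICC 0.05, a loss of 16 and 21 points against the plan's rule. Its level is still 6.5/7.1/8.5% and 5.3/5.8/6.6%.

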Cost and resource use information will be collected in all patients for the interventions (e.g., time cost for the interventions, productivity loss, enrollment in other wellness programs) and for their health care. Candidate program costs include fixed and variable costs of the ELM Intervention and Education Control. These costs

include the ELM Coach and Coach Assistant time spent delivering the program, time spent training and preparing for each group session and time spent making calls to patients between group sessions, valued at these positions' average hourly wage, group meeting costs (e.g., meeting room space, meals), printed materials, and pedometers. Candidate patient costs include the patient's time spent attending the group sessions, travel time between home and the group sessions, and productivity losses to due absenteeism and presenteeism (measured using the Work Productivity and Activity Impairment Questionnaire),¹³³ valued at the average wage adjusted for socio-demographic characteristics. Health care and wellness-related costs include the cost of primary care physician visits, emergency department visits, hospitalizations and other health and wellness provider visits.³⁴ In addition, the cost of participation in other wellness programs will be included, since ELM may be perceived as a substitute for other wellness programs that patients would otherwise engage in. Feasibility and accuracy of all data collected will be determined and a protocol for assessing costs will be developed.

Exploratory Aim 5. *To explore the impact of the ELM intervention at 12 and 24 months on selected biomarkers of CVD (hemoglobin A_{1c}, C-reactive protein, lipoprotein particle composition) and change in the social network.*

Analyses will be approached in the same way as the continuous variables outlined in Secondary Aim 3 above. Change in the social network will focus on: (1) network size; (2) frequency of contacts; and (3) overall social connectedness. We will consider use of analysis of variance with quintiles of social network summary scores¹⁴³ to identify network variables are related to MetS remission. In addition, we will specifically assess the number and frequency of contacts with other ELM participants.

Exploratory Aim 6. *To explore the acceptability of the intervention assessed as the screening to enrollment ratio, the dropout rate within each arm, and the perceived credibility of each arm.*

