The DMC will keep records of screened, enrolled, and drop-out rates. Mean differences in credibility between the 2 arms will be assessed in the same way as the continuous variables outlined in Secondary Aim 3 above.

Exploratory Aim 7. *To explore the moderating effects of built and food environment on MetS remission in the ELM Intervention and Control arms at 12 and 24 months.*

[figure not shown]
Moderating effects will be tested using logistic regression analysis (see 'Adjustment for Clustering' section above) with the dependent variable of MetS remission and the covariates of treatment arm, moderator, and the treatment-by-moderator interaction term.

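### For the continuous outcomes of Aims 3, 5 and 6, an undefined judgement of non-normality picks t-test or Mann-Whitney, both labelled comparisons of means, so the quantity tested can change with the data

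*SAP*

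**What the plan says.** SAP section 3.4.1 states: "Continuous variables will be checked for normality using Q-Q plots". Section 3.4.1.2 then names, for the case without a significant cluster effect, "the t-test (or the Mann-Whitney test if distributions are sufficiently non-normal) for the comparison of means". For the case with one, "the cluster-adjusted t-test (or the cluster-adjusted Wilcoxon Rank-Sum test if distributions are sufficiently non-normal) will be used to compare means". The section gives no threshold, does not say which distribution is inspected (raw values, changes or residuals), does not say whether the inspection is blind to arm, and assigns no test to any outcome in advance.

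In section 3.4.2, Secondary Aim 3 uses this rule: "Mean changes (from baseline to 12 or 24 months) between the two arms will be compared using the appropriate 2-sample test". Its next sentence describes something else, a model for the 12- or 24-month value with the baseline value and treatment allocation as predictors. Exploratory Aim 5 follows Aim 3: "Analyses will be approached in the same way as the continuous variables outlined in Secondary Aim 3 above". So does the credibility comparison in Exploratory Aim 6: "Mean differences in credibility between the 2 arms will be assessed in the same way as the continuous variables outlined in Secondary Aim 3".

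The primary outcome does not pass through this rule: "For each arm, the proportion of patients in remission of MetS at 12 months will be computed". Aim 2 is analysed in the same way as the primary aim.

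**The concern.** A t-test targets a difference in means. Mann-Whitney targets stochastic ordering, that is, whether a patient in one arm tends to have a higher value than a patient in the other. The two questions coincide only under an added assumption, such as equal shapes with a pure shift, and the SAP does not make it. A behavioural intervention that helps a subset of patients strongly would change the shape of the distribution, which is where the two questions part.

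Two things are at stake. First, a results table headed as mean changes could mix mean differences with rank comparisons, with the mix decided from the outcome data by an unstated criterion. Second, Aim 3 already names a baseline-adjusted model but leaves a two-sample route beside it, without saying which one supplies the reported result.

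**Working it through.** **Inputs.** The SAP states no figure for this rule, so there is nothing to reproduce. Section 3.4.3 gives 48 patients and 20% dropout. Two equal arms would hold 48/2 = 24, and 24 × 0.8 = 19.2, so about 19 completers. The same section also prints 16 per arm, so 16 is included where available. The two-sided 0.05 level is stated for the primary test only ("A two-sample, two-sided, z-test for proportions will be used to compare the rate of MetS remission between the two treatment arms") and is assumed here. The distributions, effect size and correlation below are assumptions, patients are independent, and clustering is ignored. Where a mechanical version of the switch is needed, Shapiro-Wilk p < 0.05 in either arm stands in for the undefined judgement.

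**Step 1: does the rank test compare means?** Take a centred exponential change in the ELM arm and a centred normal change in control. Both means are 0. The median of the exponential arm is SD × (ln 2 − 1), which is −0.31 for SD 1 and −0.46 for SD 1.5. The control median is 0. The means agree but the ordering does not.

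| Equal true means | n per arm | Mann-Whitney rejects | t-test rejects |
|---|---|---|---|
| Exponential SD 1 vs normal SD 1 | 19 / 24 | about 7% / 7-8% (runs vary from 6% to 8%) | about 5% (Welch) |
| Exponential SD 1.5 vs normal SD 1 | 19 / 24 | 10-11% / 12-13% | about 6% (Welch) |
| Lognormal vs normal, equal SD | 16 / 24 | 7.7% / 9.0% | 5.8% / 6.1% |

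In the lognormal case the probability that an ELM value exceeds a control value is 0.46 rather than 0.50. The two-stage rule tracks Mann-Whitney closely (10.5% and 12.5% in the SD 1.5 case), because the skew is usually detected.

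**Step 2: does the sample choose the test?** With both arms truly normal, two checks at 5% flag at least one arm with probability 1 − 0.95² = 9.75%. Simulation agrees, at about 10%. In roughly one outcome in ten, chance alone would send the analysis to the rank test.

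**Step 3: is type I error inflated in general?** No. With identical distributions in both arms (normal or skewed), the two-stage rule rejects in 4.7% to 5.4% of runs. Taking whichever test is significant would give 5.8% to 7.4%.

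**Step 4: the baseline value, a separate matter.** Assume unit SDs, correlation 0.6 and a 0.7 SD effect at 19 per arm.
- Variance of change: 2(1 − 0.6) = 0.80. Standard error of the arm difference: √(2 × 0.80/19) = 0.290.
- Residual variance after baseline adjustment: 1 − 0.6² = 0.64. Standard error: √(2 × 0.64/19) = 0.260.

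The adjusted estimate is more precise whichever two-sample test it replaces. Simulated power:

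| Errors | Plan's two-stage rule on change | Baseline-adjusted model, HC3 errors |
|---|---|---|
| Normal | about 65% | about 71% |
| Exponential | about 77% | about 73% |

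Repeat runs differ by two or three points but keep the same order. The HC3 model's own error rate is about 4%.

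**The case against.** A parametric test with a rank fallback is common practice, and applied mechanically it is nearly harmless when the arms have the same distribution. When the distributions differ, a Mann-Whitney rejection correctly rejects its own null hypothesis; only the label is wrong. The 11-13% figure needs a larger SD as well as a different shape in the ELM arm, and nothing in the SAP supports those values. Under strong skew the plan's rule is the more powerful option. A smaller repair, such as stating a criterion or assigning a test to each outcome in advance, would remove the discretion. All of this stands, and it limits the size of the point.

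Several stronger readings are tempting, but the document does not support them:
- *That the plan has the power of Mann-Whitney under normal errors, about 60% against 69% or so for the adjusted model.* The rule calls for Mann-Whitney only after non-normality is judged present, so the fair figure under normality is about 65%.
- *That the switch discards the baseline adjustment.* The t-test on changes has no baseline covariate either. Section 3.4.1.2 also lists linear regression, or its mixed version, with no normality switch, so the adjusted model is not replaced by the rank test.
- *That raw variables rather than residuals decide.* The SAP does not say which distributions are inspected. Within-arm changes are the residuals of a two-sample comparison of changes.
- *That the SAP ties the Q-Q plots to the switch.* That link is an inference, though a reasonable one, since no other check is named.

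**Conclusion.** The point holds for the continuous outcomes of Secondary Aim 3 and Exploratory Aims 5 and 6. The fault is a target quantity that can change with the data, an undefined criterion for changing it, and a rank test described as comparing means. It is not a general inflation of type I error, and it does not touch remission at 12 or 24 months.

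The size depends on assumptions the SAP cannot confirm. With equal means, rejection by Mann-Whitney runs from near 5% (identical distributions), through about 7% (exponential against normal, equal SDs; up to 9.0% for a lognormal at 24 per arm), to 11-13% (ELM SD 1.5 times control).

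The unused baseline value is a related but separate weakness: about six points of power lost under normal errors, and about four points in the plan's favour under strong skew. It is worth correcting because the SAP already contains the better-defined analysis.

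**What to change.** 1. For each continuous outcome with a baseline value, make the linear model already described in Secondary Aim 3 (baseline value and treatment allocation as predictors; mixed version where clustering is modelled) the single source of the estimate, confidence interval and p-value.
2. Name in advance how skew is handled for each outcome: robust (for example HC3) standard errors, permutation inference or a stated transformation.
3. Use Q-Q plots of the model residuals as a diagnostic only, not to select the test.
4. Report Mann-Whitney, or its cluster-adjusted version, as a sensitivity analysis described as a test of stochastic ordering.
5. For any outcome without a baseline value (credibility in Aim 6 may be one; the SAP does not say), name one comparison of means in advance.

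The cost is SAP wording and standard software options, with no new data or design change. The drawback is a few points of power for strongly skewed outcomes left untransformed, about 77% down to 73% in the scenario above.
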